3.12 Proposed research timeline

Recruitment process (see Section 3.6) will begin as soon as this study received human ethics approval. Recruitment will be ongoing until May unless target sample size has achieved. The 8-week weight-loss intervention will be running in cohorts, spanning through February and July. All cohorts and data collection are expected to complete by the end of July. Laboratory analysis of blood samples is expected to begin in June and completed in October. Data analysis and manuscript write-up is expected to begin in September and completed in December.

Table 6. A summary of proposed research timeline.

	Jan	Feb	Mar	Apr	May	Jun	Jul	Aug	Sep	Oct	Nov	Dec
Recruitment	✓	✓	✓	✓	✓							
Data collection		✓	✓	✓	✓	✓	✓					
Lab analysis						✓	✓	✓	✓	✓		
Data analysis & write-up									✓	✓	✓	✓

4. Ethics approval

Human ethics approval to conduct this study will be obtained from the Auckland Health and Disabilities Ethics Committee (HDEC), Auckland, New Zealand.

5. Trial registration

The trial will be registered with the Australia New Zealand Clinical Trials Registry (ANZCTR).

6. Risks and benefits

Controversy exists among the public regarding the advantages and disadvantages of a high protein diet. Generally, intakes that exceed the capability of liver and kidney to 'detoxify' the AA-derived nitrogenous waste should be avoided (Wu, 2016), therefore individuals diagnosed with impaired liver or kidney function are excluded from this study.

According to the Australian and New Zealand Nutrient Reference Values (NRV), there is no strict upper level of intake for protein in terms of grams per day due to insufficient evidence, but an upper level of 25% energy from protein is generally recommended for sedentary individuals (National Health and Medical Research Council et al., 2006). Importantly, the NRV is recommended on the basis of an energy-balanced diet.

Since this is a negative energy balance study, the total daily energy intake (MJ) is lower and hence a low absolute protein intake (grams). The protein intake in the intervention group is high as a percentage of total energy but when expressed as absolute protein intake (grams), the intervention diets do not exceed the recommended upper level as illustrated in Table 4.

Table 4. An example illustrating the amount of protein when expressed in percentage of total energy and in absolute term.

Total energy intake (MJ)	% energy from protein	Absolute amount of protein (g)
11.9 ¹	25% ³	178
4.8 ²	50%	144

¹Assumption of the daily energy requirement of a sedentary 130kg woman.

²Total energy intake and percentage energy from protein representing weight loss period when energy intake is restricted to 40% of daily energy requirement.

³NRV upper level of intake at energy balance.

Since the capability for liver and kidney to handle the nitrogen load is dependent on absolute intake (Bilborough and Mann, 2006), therefore our intervention diet is safe for all healthy individuals. Furthermore, a recent large international study in high risk adults showed that after a 2-month LED for weight loss, an *ad lib* high protein diet (25% energy from protein during weight maintenance, ¹as per example above) did not worsen the kidney function of overweight, pre-diabetic but otherwise healthy older adults (Moller et al., 2018). All intervention diets to be used in this current trial (HPNC, HPLC, NPNC and NPLC) have previously been shown to promote weight loss (Soenen et al., 2012) with no adverse events reported.

Both obesity and rapid weight loss have been associated with increased risk of symptomatic gallstones. Hence, LEDs have been associated with this increased risk. Participants will be monitored for adverse events throughout this 8-week intervention, and any events reviewed by the study consulting physician.

Venous cannulation may result in mild discomfort for the participant. The participant will be monitored by a research nurse throughout the day and no adverse events are expected. Participants will be continuously monitored at all CIDs and following the visits by telephone interview, over the study period, by research staff.

DXA uses a low dose of ionizing radiation, similar to the natural radiation exposure of a 1 hour airplane flight. The exposure to participants represents a very low risk. Pregnancy in female participants is an exclusion criteria, as is metal implants such as cardiac pacemakers.

7. Data collection/privacy/confidentiality

Data will be de-identified and recorded in hard copy on case report forms (CRF) and also stored in electronic format using Microsoft Excel. All hard copy CRFs will be stored in secure locked cabinets and the electronic data stored on a secure server with an automatic backup facility at the University of Auckland Human Nutrition Unit.

8. Adverse event reporting

Adverse events (AEs) are classified as serious or non-serious. The investigator is responsible for reporting and recording adverse events. An adverse event is defined as an event that is undesirable occurring in a participant, whether related or unrelated to the study procedure.

Serious adverse events (SAEs) include:

- i. Death.
- ii. Life threatening event.
- iii. Serious injury i.e. events which require hospitalisation or medical attention.

Non serious events include:

- i. All events not defined as serious.

Any reported AEs and SAEs will be recorded at the clinic visit.

9. Data retention

All data will be retained for a period of 10 years, or as stipulated by the NZ National Human Ethics Committee (HDEC).

10. Clinical trial sites

The study visits will be conducted at the University of Auckland Human Nutrition Unit (www.humannutritionunit.auckland.ac.nz) and the body composition scan (DXA) will be conducted at Department of Surgery Body Composition Unit at Auckland City Hospital.

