3.4 Participants

Inclusion criteria

- i. Females aged between 18 and 65 years.
- ii. Obese (BMI 30 kg/m² - 45kg/m²) with a maximum body weight of 130kg
- iii. Otherwise healthy

Exclusion criteria

- i. Recent body weight loss/gain >5% within previous 3 months
- ii. Currently taking part in an active diet program
- iii. Current medications or other conditions known to affect body weight and appetite
- iv. Previous bariatric surgery
- v. Diagnosed with impaired liver or kidney function
- vi. Significant current disease such as type 2 diabetes, cardiovascular disease, or cancer; or digestive disease including inflammatory bowel syndrome/disease (IBS/D), ulcerative colitis (UC), Crohn's disease
- vii. Systolic blood pressure \geq 160 mmHg and/or diastolic blood pressure \geq 100mmHg
- viii. Depression or any other anxiety disorder known to affect appetite
- ix. Unable to consume food items included in the study, or hypersensitivities or allergies to these foods (based on Food Preference Questionnaire)
- x. Smokers or ex-smokers who have given up smoking for less than 6 months
- xi. Pregnant or breastfeeding women
- xii. Unwilling/unable to comply with the study protocol

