3.6 Participant recruitment and pre-screening

Recruitment of participants will be conducted in the Auckland region using convenient sampling method. Participants will be recruited through various media, by posting the ethics-approved advertisement on newspapers, press release, email, social gatherings, public notice boards, blog sites and medical centres. Participants who completed previous studies at HNU will be invited back for this study if they wish to participate.

Individuals who are interested in this study may contact the investigators for a remote pre-screening (either online questionnaire or telephone interview) and a Participant Information

Sheet (PIS), which will be emailed or posted to them. Data on age, ethnicity, reported body weight and height, brief medical record, current medications will be collected during the pre-screening to ensure that inclusion/exclusion criteria are met before attending Human Nutrition Unit (HNU) for a screening visit.

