3.7 Clinic visits

The summary of the screening and clinical investigation days (CIDs) are shown in Table 5. Participants are required to attend all visits.

Table 5. Agenda during each visit at HNU.

Agenda	Screening	Baseline	8-week weight loss	
		CID 1 Week 0	CID 2 Week 4	CID 3 Week 8
Informed consent	✓			
Anthropometric measurement ¹	✓	✓	✓	✓
Blood pressure	✓	✓	✓	✓
Fasting blood sample	✓	✓	✓	✓
24-hour urine		✓	✓	✓
4-day food record		✓	✓	✓
DXA		✓		✓
Preload challenge		✓		✓
3-factor eating questionnaire		✓		✓
Baecke Questionnaire		✓		✓
Dietary consultation		✓	✓	✓

¹ Anthropometric measurements include body weight, body height and waist/hip circumference.

Screening visit

During the screening visit, participants are required to arrive at HNU after an overnight fast of at least 10 hours, having consumed nothing but water since the prior evening meal.

Participants will receive a Participant Information Sheet (PIS) and the study will be explained by a researcher. Participants will be given the opportunity to ask questions and written informed consent will be obtained. Participants will then be screened for eligibility. Demographics (age and ethnicity) and anthropometry (height, body weight, waist and hip circumference, BMI and blood pressure) will be recorded. A venous blood sample will be collected to check for fasting plasma glucose (FPG) concentration on site to screen for diabetes. When FPG is ≥ 7.0 mmol/L, another venous blood sample will be collected to check for HbA1c. When HbA1c ≥ 50 mmol/L, participant's GP will be contacted to confirm whether the participant has diabetes.

After confirming the participant's eligibility, participants will be given a urine bottle, alongside verbal and written instruction on how to collect urine samples. Additionally, participants will be taught to complete a 4-day food record (3 weekdays and 1 weekend) by investigators. Participants are asked to collect the urine sample on one of the days of the food record. The urine samples and 4-day food records will be completed during the week before attending CID1 and CID 3.

Clinical Investigation Days (CIDs)

For all CIDs, participants are required to arrive at HNU after an overnight fast of approximately 10 hours, having consumed nothing but water since the prior evening meal.

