3.12 Blood and urine parameters

Fasting blood samples

- i. Hb_{A1c}
- ii. Glucose (FPG)
- iii. Cholesterol (total-C, LDL-C, HDL-C) and triglyceride
- iv. Liver function (AST, ALT, ALP, GGT)
- v. CCK, GLP-1, PYY, GIP, insulin, C-peptide, glucagon and amylin
- vi. Amino acids

Postprandial blood samples (a subset of participants during preload-test meal challenge only)

- i. Glucose
- ii. CCK, GLP-1, PYY, GIP, insulin, C-peptide, glucagon and amylin
- iii. Amino acids

Urine parameters (for the assessment of protein intake compliance)

- i. Urine nitrogen

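### Section 6 names nitrogen load on liver and kidney as the hazard of the high-protein diets, but no renal marker is listed at any visit and no reading of the liver enzymes before or during the diet is stated

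*Protocol*

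**What the plan says.** **The hazard.** Section 6 (Risks and benefits) cautions: "Generally, intakes that exceed the capability of liver and kidney to 'detoxify' the AA-derived nitrogenous waste should be avoided". It then gives the entry control: "therefore individuals diagnosed with impaired liver or kidney function are excluded from this study". The matching exclusion criterion in section 3.4 reads "Diagnosed with impaired liver or kidney function", with no laboratory threshold.

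**How eligibility is checked.** Section 3.6 takes history remotely, by online questionnaire or telephone; the items include "brief medical record, current medications will be collected during the pre-screening". At the screening visit (section 3.7), "A venous blood sample will be collected to check for fasting plasma glucose (FPG) concentration on site to screen for diabetes". HbA1c follows if fasting glucose is 7.0 mmol/L or more, and the participant's GP is contacted if HbA1c is also high. No liver or kidney test is described for eligibility.

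**What is measured.** The section on blood and urine parameters (the first of two numbered 3.12) lists four liver enzymes (AST, ALT, ALP, GGT) among the fasting analytes. It lists no creatinine, eGFR or blood urea. The single urine analyte is nitrogen, labelled as a check on protein intake compliance. Table 5 schedules fasting blood at screening and at weeks 0, 4 and 8, but the analyte list is not tied to visits.

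**When it is analysed.** The proposed timeline (the second section 3.12) runs the diet in cohorts from February to July. It then says: "Laboratory analysis of blood samples is expected to begin in June and completed in October". Table 6 shows the same months and makes no exception for any analyte.

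**The concern.** The protocol identifies two organs as the limit on how much protein is acceptable, then keeps out only women whose impairment is already known. A woman with undiagnosed, symptom-free renal or hepatic impairment passes every check the protocol describes. If allocated to a high-protein arm, she is assigned a plan of 118 or 138 g protein a day for 8 weeks (Appendix 1). Her kidney function is never measured, and nothing ensures that her liver result is seen before or while she follows the diet.

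What is at stake is participant safety and the value of blood already being taken. The primary outcome, the power calculation and the comparison of diets are not affected.

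**Working it through.** **1. Reproduce the protocol's own safety figures.** Section 6 compares protein at energy balance with protein on the diet. Grams = energy × protein share ÷ energy per gram. The factor 16.7 kJ/g is my assumption (about 4 kcal/g).

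- Reference: 11,900 kJ × 0.25 ÷ 16.7 = 178 g, as stated.
- High-protein diet: 4,800 kJ × 0.50 ÷ 16.7 = 144 g, as stated.
- At 17 kJ/g the two figures are 175 g and 141 g, so the comparison does not depend on the factor.
- For any plan set at exactly 40% of requirement, the ratio is 0.40 × 0.50 ÷ 0.25 = 0.80. The example is therefore not peculiar to the 130 kg woman it uses.

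The arithmetic is sound. It compares an intake with a general upper level and says nothing about whether a particular woman's organs are normal.

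**2. Set the exclusions side by side.**

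| Exclusion (section 3.4) | Test described at screening (section 3.7) | Marker listed in blood and urine parameters |
|---|---|---|
| Type 2 diabetes | Fasting glucose on site; HbA1c if 7.0 mmol/L or more; GP contacted if HbA1c is also high | Glucose, HbA1c |
| Impaired liver function | None stated | AST, ALT, ALP, GGT; time of reading not stated |
| Impaired kidney function | None stated | None |

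For diabetes the protocol does not rely on a prior diagnosis. For the two organs that section 6 names, it does.

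**3. Count who is concerned.** Section 3.5 recruits 35 women per arm. Two high-protein arms give 2 × 35 = 70 of 140. Table 5 schedules four fasting bloods per woman, so 4 × 70 = 280 draws in those arms if nobody drops out. Renal markers listed for them: none.

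**4. Check the timing.** The diet runs February to July; the stated laboratory work runs June to October. Suppose the liver enzymes are in that work. A woman who starts on 1 February ends week 8 in late March, and her baseline result comes no earlier than 1 June, about 120 ÷ 7 = 17 weeks after it was drawn. The supposition is not settled by the text: the protocol does not say whether the enzymes are batched or read as they arrive.

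**The case against.** Four objections deserve weight.

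**The June date.** A reader might infer that no blood is analysed before June, and go on to calculate what share of women would finish the diet before any liver result exists. The documents do not support that. Fasting glucose, and HbA1c when triggered, are obtained for screening, and both stand on the same fasting list as the liver enzymes. So that list is not wholly confined to the June to October work, and the timeline is in any case described as proposed. A share would also need cohort sizes, which are not given, and would count all four arms although the hazard belongs to the high-protein diets. What stands is that no reading time for the enzymes is stated.

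**Other safeguards.** A reader might infer that the exclusion is the protocol's only answer to the hazard, or that harm would go unseen. Neither is right. Section 6 also relies on absolute intake, on a study of kidney function after a low energy diet, and on earlier use of these diets with no adverse events reported. Section 3.4 requires women to be otherwise healthy. Adverse events are monitored throughout and reviewed by the study consulting physician. These are real protections, but none shows symptom-free impairment in an individual. The cited kidney evidence concerns 25% of energy from protein during weight maintenance, not 50% during the low energy diet.

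**The safety sentence.** Section 6 says "therefore our intervention diet is safe for all healthy individuals". A reader might fault the trial for not collecting data to prove this. It is a rationale given before the trial, not a conclusion to be drawn from it, and organ safety is not among the outcomes. The narrower point stands: the sentence presupposes healthy organs, and no stated entry test looks at them.

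**No promise is broken.** No section undertakes renal testing, so this is not a direct contradiction. It is a mismatch between a hazard the protocol names and the checks it fixes. The analyte list, eligibility checks and laboratory timing are all set in this protocol, so they are not details awaiting an analysis plan.

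**Conclusion.** The point holds in a limited form. Entry control specific to liver and kidney depends on an existing diagnosis. No renal marker is listed for any of the 140 women, of whom 70 are planned for high-protein diets. Liver enzymes are sampled, but no reading before or during the diet is stated. Asymptomatic impairment could be missed at entry and during the diet: for the kidney throughout, and for the liver possibly until the batch analysis.

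The kidney part rests on the text alone. The liver part rests on the absence of a stated reading time, together with a laboratory schedule that starts after much of the diet period. Whether the enzymes actually wait for June is unknown. The number of women with undiagnosed impairment cannot be estimated from the documents, and no harm rate is claimed. This should be corrected because the hazard is the protocol's own and the blood is already drawn.

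**What to change.** Reconcile sections 3.4, 3.7, both sections numbered 3.12 and section 6:

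- **Blood and urine parameters:** add a renal marker, for example creatinine, to the fasting panel, and state at which visits it and the liver enzymes are measured.
- **Section 3.7:** state when the liver and renal results are read relative to the start of the diet.
- **Proposed timeline:** separate these safety analytes from the June to October batch, leaving the hormones and amino acids there, and send the results to the study consulting physician.
- **Sections 3.4 and 6:** make the wording of the exclusion and of the safety argument agree with whatever testing is adopted. Any eligibility or action limit is for the sponsor and the study physician to set; none is proposed here.

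The cost is one low-cost analyte on existing draws, at most 4 × 140 = 560 assays for enrolled women plus those who fail screening, and non-batched runs for the safety panel. Fasting blood is already scheduled at all four visits, so no extra visit or blood draw is needed.

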At CID1 (Week 0), the visit will take approximately 5 hours. Participants are required to arrive at HNU at 8am for a preload challenge (see Section 3.7). After the preload challenge, participants will be given a lunch meal. Participants are also required to complete a 3-factor eating questionnaire (3FEQ) and a Baecke Questionnaire. It will be followed by a dietary consultation session with an investigator. Finally, participants will be invited to the Auckland City Hospital to perform a body composition scan using DXA (see Section 3.9). The 8-week weight loss intervention period will be commenced after CID1, whereby participants are required to adhere to their assigned intervention diets (HPNC/HPLC/NPNC/NPLC). The intervention comes to the end upon the completion of CID3.

At CID 2 (Week 4), the visit will take approximately 30 minutes. Participants are required to arrive in the morning at any time between 8:00am and 11:00am for their anthropometric measurements to be taken, following by blood pressure. Then a Research Nurse will collect 7mL of fasting blood. Finally, there will be a dietary consultation session with an investigator.

At CID 3 (Week 8), the visit itinerary will be the same as CID 1. The study is completed upon the end of CID 3 visit.

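### Section 8 classes any event needing medical attention as serious, and ties AE recording to the clinic visit with no stated route for events learned between visits or in women who stop attending

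*Protocol*

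**What the plan says.** Section 8 (Adverse event reporting) divides events into serious and non-serious. Serious covers death, a life-threatening event and a third item: "Serious injury i.e. events which require hospitalisation or medical attention". Non-serious is simply the remainder: "All events not defined as serious". On timing it has one sentence: "Any reported AEs and SAEs will be recorded at the clinic visit". It gives the investigator both the reporting and the recording duty, but names no time limit and no recipient for an SAE report.

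Section 6 (Risks and benefits) describes wider surveillance. It names a harm relevant to this intervention: "Both obesity and rapid weight loss have been associated with increased risk of symptomatic gallstones". It then states: "Participants will be monitored for adverse events throughout this 8-week intervention, and any events reviewed by the study consulting physician". It adds: "Participants will be continuously monitored at all CIDs and following the visits by telephone interview, over the study period, by research staff".

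Section 3.7 and Table 5 place the clinical investigation days (CIDs) at weeks 0, 4 and 8. Of the last one, Section 3.7 says: "The study is completed upon the end of CID 3 visit". Between CIDs there are group meetings at weeks 0, 2, 4 and 6 (Section 3.9, Group meetings) and telephone calls from investigators (Section 3.9, Compliance). The meetings are described as counselling and the calls as enquiries about diet. Neither is given an AE task.

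**The concern.** Two rules in Section 8 work badly if staff follow them as written.

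The first is the definition of serious. The third item sets a threshold that many minor events can cross, and non-serious has no content of its own, so an error in one class is an error in both. An SAE count on this basis would not tell a safety reader how many women were seriously harmed.

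The second is the recording rule. Section 6 provides for events to come to light between visits, while Section 8 provides only for writing them down at a visit. An event mentioned by telephone has no stated place in the record until the next CID, and a woman who stops attending has no next CID. Women who leave because of an event are the ones whose events matter most to the safety record.

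**Working it through.** No statistical figure in the plan concerns adverse events, so the check is mainly a reading of the sections against one another, with simple arithmetic on timing and dropout.

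**1. The definition.** The third item uses i.e., which equates serious injury with what follows it, and what follows joins two conditions with *or*. Applied to three kinds of event:

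| Event | Meets the third item as worded? | Class |
|---|---|---|
| Hospital admission for gallstones | Yes, hospitalisation | Serious |
| Gallstone symptoms managed by a doctor without admission | Yes, medical attention | Serious |
| Event needing neither | No | Non-serious |

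The first two rows cannot be told apart in an SAE count. Non-serious is left holding only events that needed no medical care.

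**2. Recording delay.** Inputs: CIDs at weeks 0, 4 and 8 (Section 3.7, Table 5).

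- Longest gap between CIDs: 4 weeks × 7 = 28 days.
- Mean delay if onset is uniform over the gap (an assumption): 28 / 2 = 14 days.
- If the group meetings were also recording points, contacts would fall at weeks 0, 2, 4, 6 and 8. The longest gap becomes 14 days and the mean 7 days. Using the telephone calls as well could shorten this further, but the protocol does not give their frequency.

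These are delays in recording, and only if Section 8 is followed literally.

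**3. Women who stop attending.** Inputs: 35 recruited per arm, 4 arms, 10% dropout (Section 3.5).

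- Recruitment target: 35 × 4 = 140, as stated.
- Expected dropouts: 0.10 × 140 = 14, or 14 / 4 = 3.5 per arm.

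Fourteen is an upper bound on the women affected at that dropout rate. It counts dropout for any reason. Some of these women will have no event, those who leave after week 4 will already have had CID2, and telephone contact may reach others.

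**4. After CID3.** Three statements bear on this. AE monitoring covers the 8-week intervention (Section 6). The study is complete when CID3 ends (Section 3.7). Telephone interviews follow the visits, over the study period (Section 6). If the visits include CID3, a call comes after it. If the study period bounds the calls, none does. CID3 repeats the CID1 itinerary, including cannulation in the consenting subset (Section 3.8), so the uncertainty falls just after the last invasive procedure. The protocol states no AE-collection window that would settle it.

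**The case against.** The best defence is that Section 8 says only where reported events are written down. It does not limit detection, reporting or medical review. Section 6 provides monitoring throughout and physician review of any event. Section 3.9 adds calls and lets participants contact investigators between visits. Section 8 itself separates reporting from recording and ties only recording to the visit. This stands. A reader might infer that events are collected only at clinic visits, or that physician review of a gallstone event could wait 28 days. The text does not say *only*, and review is not tied to a CID. What remains is a missing link between Sections 6 and 8.

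It can also be said that the third item is headed serious injury and covers events that require care, so a routine consultation would not qualify. That narrows the reading but does not rescue the wording, because an event that does require outpatient care still qualifies. It does rule out sizing the problem from the share of women who see a doctor for any reason. An assumed 5–20% would give 7–28 of 140, but that is a different quantity, and the documents give no rate for it.

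Finally, Section 3.11 lists no safety outcome and no comparison of harm between arms, and the primary outcome is body weight. So the documents do not support a claim that a planned arm comparison is biased, and the primary result is untouched. A separate safety procedure may also exist, although Section 8 cites none.

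**Conclusion.** The point holds in two parts, with a third matter unclear.

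- **Definition.** As worded, outpatient care and hospital admission fall in the same class, and the serious/non-serious split is not interpretable. This rests on the text alone. It is a defect within Section 8, not a conflict with Section 6, which offers no definition of its own.
- **Recording.** Sections 6 and 8 need to be reconciled. Recording may run up to about 28 days late. Events in women who stop attending may not be recorded, with about 14 of 140 women as the ceiling if dropout is the planned 10%. Both are possible consequences of following Section 8, not losses that the protocol declares.
- **After CID3.** A reader might infer that AE collection closes when CID3 ends, with zero days of follow-up. That goes beyond the text: no window is stated, and the telephone interview after the visits could be read to include CID3. The defect is that the protocol leaves this open.

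The effect is on the quality and completeness of the safety record. The change should be made, because it is specific and costs almost nothing.

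**What to change.** 1. In the third item of the SAE definition in Section 8, delete the alternative of medical attention, so that serious injury rests on hospitalisation or an equivalent medically important event.
2. Replace the recording sentence in Section 8 so that AEs are recorded at every contact that already exists (telephone calls, group meetings and CIDs), and in a call to each woman who stops. State that SAEs are passed to the investigator and the study consulting physician when staff become aware of them.
3. State whether the telephone interview in Section 6 applies after CID3, and so when AE collection ends. A dated follow-up call some weeks later would be a preference; no figure in the protocol fixes its timing.

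The cost is revised wording, an AE page for telephone and group contacts, and a little extra staff time. The visit schedule, the diets and the sample size do not change.
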